7.1 Design

Multicentre, pragmatic, randomised, double blind controlled trial.

7.2 Setting

Delivery Suite of approximately 30 Maternity Units within the UK.

7.3 Inclusion criteria

- Nulliparous women with singleton cephalic pregnancy at term (37-42 weeks gestation)
- Confirmed delay in labour and ruptured membranes for whom the clinical decision has been made to prescribe Syntocinon for augmentation of labour

According to NICE guidance [NICE 2014], labour is established when there are regular painful contractions and progressive cervical dilation from 4 cm. Delay is suspected when cervical dilation of

< 2 cm in 4 hours occurs once labour is established. Delay is confirmed when progress of <1 cm in 2 hours is found on repeat vaginal examination.

7.4 Exclusion criteria

- Multiparous women
- Nulliparous women who:
 - have reached full dilation of the cervix (10cms)
 - are undergoing induction of labour
 - have a BMI >40 at booking
 - have a multiple pregnancy
 - have existing cardiac disease, bleeding disorders, diabetes (either pre-existing or gestational), previous uterine surgery
 - have had significant antepartum haemorrhage
 - are under 16 years of age
 - have a known contra-indication to oxytocin therapy as listed in the Summary of marketing Product Characteristics (SPC)

7.5 Identifying potential participants

Women are only eligible for the trial if they become delayed in labour. Therefore, in the first instance, arrangements will be made for all nulliparous women to receive written information about the trial during the antenatal period, ideally at about 34 weeks. This will be in the form of a letter introducing the trial and will include a Participant Information Leaflet. This will facilitate a discussion about the trial at the visit with the midwife at 35-37 weeks.

This will be organised by the participating sites, through the Research and Development Departments, to suit their local practices. If a woman decides before labour she does not wish to take part, this will be recorded in her maternity notes and she will not be approached in labour. All women will have the opportunity to ask questions about the trial and to have their questions answered. Posters will be designed for use in the antenatal and intrapartum period.

7.6 Obtaining informed consent

When a nulliparous woman is admitted to the labour ward potential inclusion will be checked by the midwife responsible for her care, with final eligibility determined by an obstetrician. If appropriate the trial will be discussed as her labour progresses, but raising the possibility of abnormal labour with women who are labouring normally may not be appropriate.

In line with NICE guidance once a woman is in established labour (i.e. she has regular painful contractions and her cervix is 4cms or more dilated on examination) assessment of progress includes cervical dilation as well as descent and rotation of the baby's head and changes in the strength, duration and frequency of uterine contractions. Should delay be suspected (when cervical dilation of <2cm in four hours is found) the woman remains under the care of a midwife. During the two hour period until progress is re-assessed the midwife is likely to suggest interventions which would facilitate progress occurring. She would encourage the woman to mobilise, consider hydration (e.g. a sports drink), and discuss appropriate and effective pain relief. If her membranes are still intact,

artificial rupture (amniotomy) will also be advised. It is during this two hour window that the HOLDS trial would be discussed and so the midwives role in introducing the trial and answering any questions she may have is vital.

Once delay is confirmed transfer to obstetric-led care would take place (if required) for an obstetric review and a decision about management, including the use of oxytocin. Once more the midwives' role is fundamental in ascertaining if the woman is potentially eligible, explaining the trial, answering any questions she may have and in providing continuous support.

It is acknowledged that if the woman, for whatever reason, is not able to give informed consent, recruitment is not appropriate. It may not be suitable for women in labour to be provided with lengthy information and so a summary of the trial will also be provided. After birth, information about the trial will continue to be given as and when requested.

Confirming eligibility and obtaining consent to participate should be performed by someone with appropriate Good Clinical Practice (GCP) training and the oxytocin will be prescribed by an obstetrician. The midwives will receive appropriate and relevant training on the study protocol, and safety reporting mechanisms for the study to enable them to introduce the trial, answer any questions, randomise the woman and record dispensing of the trial Investigational Medicinal Product (IMP). She/he would then continue to manage the woman as care is not different between the two trial arms. The administration of IMP, and clinical care would normally be undertaken by such clinical midwives and therefore falls within their normal sphere of clinical practice. Therefore, the dispensing of the oxytocin can be recorded in the trial drug reconciliation chart by the midwife responsible for the woman's care and not necessarily by an obstetrician. The only difference is the strength of oxytocin and allocation is double blinded to participants, clinicians and the research team.

The qualitative work undertaken in the pilot study indicates that the recruitment processes and information provided are acceptable to women¹. Information regarding the study is given to potentially eligible women during the late antenatal period, with access to more detailed information (on the website or by request). As described previously, discussion of the trial begins when delay is suspected but consent can only be obtained once delay in labour is confirmed. The time-window for treatment to be started is relatively short as it is between diagnosis of delay and commencement of the oxytocin (which is the recommended treatment).

7.7 Informing the participants GP

Following the participant giving consent, her GP will be notified using the trial template 'Letter to GP', and a copy kept in the site file.

7.8 Co-enrolment

Women participating in the HOLDS study cannot join other interventional trials of an IMP or procedure for delay in labour. They may be recruited to other intrapartum IMP studies. Women may be recruited to non-interventional trials such as observational or qualitative studies for delay in labour and to all other trials in pregnancy or the postnatal period.

8 Randomisation

Randomisation will be by telephone via an automated secure system developed by the Health Services Research Unit at Aberdeen University. Eligibility will be confirmed as part of the recruitment process and checked by the automated telephone randomisation system. Although some identifiable data is provided it is insufficient to constitute personal identifiable data.

Randomisation will be available 24 hours a day. Participants will be randomised at the level of the individual in a 1:1 ratio to either standard dose regimen oxytocin or high dose regimen oxytocin. A minimisation algorithm will be used to ensure balance in the allocation over the following variables:

- degree of cervical dilation in cm (<6/>=6);
- age in years (<20/>=20 to <30/>=30 to <40/>=40);
- maternity unit

A 'random element' will be included in the minimisation algorithm so that each patient has a probability (unspecified here) of being randomised to the opposite treatment that they would have otherwise received.

Resupply of subsequent treatments, should they be required, will be by the same secure system to guarantee allocation to the same dose as initial randomisation.

8.1 Treatment allocation

The trial will compare the standard dose regimen of oxytocin with a high dose regimen. NICE guidance recommends a standard dose regimen of oxytocin (2mU/min increasing every 30 minutes to a maximum 32mU/min). The comparator is high dose regimen (4mU/min increasing every 30 minutes to a maximum of 64mU/min). The high dose regimen (i.e. double the concentration) has a higher starting dose, earlier attainment of conventional maximum doses (at 2 hours rather than over 4 hours) and the possible use of higher maximum doses of oxytocin compared to the standard regimen.

Women randomised to the standard dose will receive a solution containing 2 x 5iu ampoules in 50mls (see Table 1) or 500mls (see Table 2) and those to the high dose a solution containing 2 x 10iu in 50 mls (see Table 1) or 500mls (see Table 2). Ampoules are manufactured as 5 and 10 iu and these regimens have been selected to enable the trial to be double-blinded. It is cheap (£2 per treatment) and licensed for this specific use in pregnancy- we intend to use it marginally outside the recommended maximum dose (shaded area). Synthetic oxytocin is manufactured by Novartis and called Syntocinon [®].

The standard dose regimen includes 2 ampoules of 5iu oxytocin and the high dose 2 ampoules of 10iu oxytocin with 50mls (or 500mls) of normal saline to ensure double blinding. Ampoules are only manufactured in 5 and 10iu and treatment packs contain 2 ampoules and will be stored in a fridge on Delivery Suite. Once made up the expiry time for the infusion is 24 hours.

The trial treatment packs may be stored in a separate fridge or in a designated compartment labelled for 'drugs to be used in HOLDS trial' depending on the conditions of the participating hospital's R&D approval. The fridge temperature should be maintain at 2-8C but no special monitoring arrangements are required. As the Summary of Product Characteristics indicates that Oxytocin can

be stored at 30°C for up to 3 months before being unusable, brief and small temperature excursions do not require quarantining of the IMP. Full instructions for IMP handling will be provided in a Pharmacy Manual.

A record will be kept of trial drugs dispensed. A trial-specific, structured dispensing log is provided to record the date and trial number against the treatment pack. An obstetrician will prescribe the IMP as 'Oxytocin for HOLDS study' on the participant prescription chart.

The attending obstetrician, clinical midwife or research midwife administering the randomised IMP will be required to record the initial dose and dose escalations on the Labour form.

8.2 IMP accountability and monitoring compliance

The local clinical trial pharmacist will be responsible for the storage and re-stocking the fridge on Delivery Suite. Pack usage will be monitored centrally by the Trial Office and stock sent from Sharps to the trial site. Pack use will be recorded by the recruiting site and monitored and reviewed by the trial office. Should packs be wasted for whatever reason they should be returned to pharmacy and removed from the computer system.

Table 1: Regimens	proposed	by HOLDS dilut	ed in 50mls
Table Integniterio	proposed	Sy HOLDO and	

		Dose of oxytocin (mU/	′min)
Time after starting	Infusion rate	Standard strength	High strength
(mins)	(mls per hour)	10 iu in 50mls	20iu in 50mls
0	0.6	2	4
30	1.2	4	8
60	2.4	8	16
90	3.6	12	24
120	4.8	16	32
150	6.0	20	40
180	7.2	24	48
210	8.4	28	56
240	9.6	32	64

		Dose of oxytocin (mU/min)		
Time after starting	Infusion rate	Standard strength	High strength	
(mins)	(mls per hour)	10 iu in 500mls	20iu in 500mls	
0	6	2	4	
30	12	4	8	
60	24	8	16	
90	36	12	24	
120	48	16	32	
150	60	20	40	
180	72	24	48	
210	84	28	56	
240	96	32	64	

Table 2: Regimens proposed by HOLDS diluted in 500mls

8.3 Care of women following randomisation until birth

Delay in labour is an everyday occurrence on UK Delivery Suites and intravenous infusion of oxytocin has been the treatment employed since the 1960s. It is licensed for this specific indication. The dose is titrated against the strength and frequency of uterine contractions, taking into account fetal wellbeing using cardiotocograph monitoring (fetal heart rate patterns), with the desired outcomes being re-establishment of effective uterine contractions, dilation of the cervix and vaginal birth. Obstetricians and midwives are used to managing women receiving intravenous oxytocin so, although the randomised design is double blinded, the clinical team on duty are very unlikely to encounter unfamiliar clinical problems.

The safety of mother and baby receiving oxytocin are routinely addressed by more intense monitoring than normal labour by the midwife and obstetrician caring for the woman. Routine care in labour is recommended by NICE Guidance⁵ and would normally include one-to-one care from a midwife, support and effective pain relief, frequent monitoring of the strength and frequency of contractions, the observations of the woman's vital signs (hourly pulse and four hourly temperature and blood pressure) and her fluid balance.

Continuous Electronic Fetal Monitoring (CEFM) to detect signs of developing fetal hypoxia is always used in the presence of oxytocin. Non-reassuring or abnormal features of the fetal heart rate pattern would be recorded according to NICE guidance and a fetal blood sample obtained when indicated to assess the fetal condition (current best practice). Usual care is detailed below:

- if the fetal heart rate (FHR) trace is normal, oxytocin may be continued until the woman is experiencing 4 or 5 contractions every 10 minutes. Oxytocin should be reduced if contractions occur more frequently than 5 contractions in 10 minutes,
- if the FHR trace is classified as non-reassuring, this should be reviewed by an obstetrician and the oxytocin dose should only continue to increase to achieve 4 or 5 contractions every 10 minutes,
- if the FHR trace is classified as abnormal, oxytocin should be stopped and a full assessment of the fetal condition undertaken by an obstetrician before oxytocin is recommenced.

Should either uterine tachysytole (defined as more than 5 contractions in 10 minutes for 20 minutes) or uterine hyperstimulation occur (defined as tachysystole with non-reassuring or abnormal fetal heart rate) this will be documented and obstetric opinion sought. In these situations oxytocin would be reduced, stopped or tocolysis commenced as is usual practice. The rate of reduction of oxytocin,

should that be required for any reason, will depend on clinical circumstance and should follow normal clinical practice.

Following commencement of oxytocin current NICE guidance advises the woman to have a vaginal examination 4 hours later (unless otherwise indicated). If cervical dilatation has increased by less than 2 cm after 4 hours of oxytocin, further obstetric review is required to assess the need for Caesarean section. If cervical dilatation has increased by 2 cm or more, labour is allowed to progress with vaginal examinations as per local routine practice.

The care pathways for the women are identical regardless of the randomly allocated dose regimen of oxytocin; the only difference is the concentration of the oxytocin they receive. Participating in the study will not alter the care the woman or baby receives should any anticipated or unanticipated problem occur, and standard procedures, as defined within the local Maternity Unit protocols, would then be followed.

8.4 Breastfeeding

There are no restrictions on breastfeeding for women recruited to the HOLDS trial.

Process	Time	CRF	Person responsible
Confirm eligibility	When delay confirmed	Randomisation form	GCP and HOLDS trained obstetrician
Consent	Following confirmation of eligibility	Consent form	GCP and HOLDS trained obstetrician or midwife
Randomisation telephone call	Following confirmation of consent	Complete randomisation form	HOLDS trained obstetrician, midwife, student midwife or Maternity Support Worker
Prescription of drug	Following randomisation	Prescription chart	HOLDS trained obstetrician
Study treatment allocation	Following prescription of drug	Randomisation form and in medical notes	HOLDS trained midwife or obstetrician
Labour data collection	From commencement of study treatment until after birth	Labour form	HOLDS trained midwife
Birth outcome data collection	After discharge	Birth and discharge form	HOLDS midwife

8.5 Summary of HOLDS data collection points and personnel

8.6 Unblinding of trial participants

Unblinding of participants will not normally be necessary. Any adverse event that occurs from whichever trial treatment the woman is randomised to should be managed by the clinical team caring for the woman as per local protocols. The plasma half-life of oxytocin is approximately five

[figure not shown]
minutes, so should any cause for concern be identified, stopping the oxytocin is the most common and effective treatment rather than unblinding. However should this be required unblinding codes will be held in BCTU, with access through the local PIs and research midwives. Reasons for unblinding will be documented.

8.7 Withdrawal of trial/treatment or protocol violation

If a woman decides, after randomisation, she does not wish to be part of the trial, or there is a protocol violation, she will be withdrawn from the trial and will receive the standard dose oxytocin regimen using non- trial treatment. The timing of randomisation is as close as possible to the commencement of treatment so this should minimise the number of post-randomisation withdrawals or violations. The dose of oxytocin is titrated against uterine activity and the fetal heart rate, so it may be temporarily stopped and re-started as described in Section 8.3 above. Clear distinction will be made as to whether a participant is withdrawing from the trial but will still be followed up on an intention-to-treat basis, or whether the participant refuses any follow-up. If a participant explicitly withdraws consent to have any further data recorded their decision will be respected and recorded. All communication surrounding the withdrawal will be noted in the woman's hospital records and trial database, and no further data will be collected for that woman. If an SAE has occurred before her withdrawal we will follow this up to completion of the event.

Should a woman lose capacity to provide continued consent, they will be assumed to wish to remain in the HOLDS trial as there would be no further procedures or tests required for the trial.

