10.2.2 Expected ARs for labour outcomes

There are a number of expected ARs for labour outcomes listed in section 4.8 of the SPC (see Appendix 1 & 2), which are considered to be of 'not know' frequency (i.e., isolated reports that cannot be estimated from the available data) and for convenience are listed, but are not limited to, below:

- uterine tachysytole (defined as more than 5 contractions in 10 minutes for 20 minutes)
- uterine hyperstimulation (defined as tachysystole with non-reassuring or abnormal features of the fetal heart rate)

Our pilot study found that 17% of the standard dose group (8/47) had an episode of uterine tachysystole with 11% (5/47) experiencing hyperstimulation. With our proposed sample of 1,500 women, we would have 80% power to detect an absolute increase of 6% in the rate of tachysystole (i.e. 17% to 23%) and a 5% increase (i.e. 11% to 16%) for hyperstimulation.

ARs occurring in labour will be recorded on the Labour Form. Occurrence will be confirmed by the local obstetrician and midwife, recorded on the CRF and returned to the Trial Office. They will be reported to the DMC when it meets.

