12.2 Statistical analysis

A separate Statistical Analysis Plan will provide a detailed description of the planned analyses. A brief outline is given below.

Point estimates, 95% confidence intervals and p-values from two-sided tests will be calculated for all main outcome measures. Outcome will be adjusted for the minimisation variables. Analysis will be of all randomised subjects in the intention to treat population.

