12.2.3 Missing Data/Sensitivity Analyses

Every attempt will be made to collect full follow-up data on all women (unless a woman withdraws consent for follow-up data collection). In particular, participants will continue to be followed-up even after any protocol treatment deviation or violation. It is thus anticipated that missing data will be minimal. Participants with missing primary outcome data will not be included in the primary analysis. This presents a risk of bias, and secondary sensitivity analyses will be undertaken to assess the possible impact of the risk. This will include a worse-case assumption that those women missing the primary outcome had a caesarean section. Other sensitivity analyses will involve simulating missing responses using a multiple imputation (MI) approach.

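### Section 8.7 moves every protocol violator to non-trial standard-dose oxytocin, which dilutes the dose contrast in the high-dose arm only; the wording should let allocated treatment continue where nothing requires it to stop

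*Combined protocol and SAP*

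**What the plan says.** Section 8.7 covers two events in one sentence: the woman changes her mind after randomisation, "or there is a protocol violation, she will be withdrawn from the trial and will receive the standard dose oxytocin regimen". The replacement oxytocin is non-trial stock. The section neither defines nor grades a violation, and no other section says that trial treatment may continue after one.

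On follow-up the protocol is clear elsewhere. Section 12.2.3 states that "participants will continue to be followed-up even after any protocol treatment deviation or violation". Section 12.2 states: "Analysis will be of all randomised subjects in the intention to treat population". Section 8.7 itself asks sites to distinguish "whether a participant is withdrawing from the trial but will still be followed up on an intention-to-treat basis" from refusal of all follow-up, and it ends data collection only when a woman explicitly withdraws consent for it.

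On recording, the data collection table (8.4/8.5) gives the timing of labour data as "From commencement of study treatment until after birth". Section 8.1 says that the person "administering the randomised IMP will be required to record the initial dose and dose escalations on the Labour form". Section 10.2.2 adds that "ARs occurring in labour will be recorded on the Labour Form".

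**The concern.** A woman's decision to leave must be respected whatever it costs the trial. A protocol violation is a different matter: it is an event to record, and under intention to treat it is not by itself a reason to change her treatment. Section 8.7 joins the two, with two results.

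- **Wording.** A site that reads only 8.7 is told that a violator is withdrawn from the trial. A site that reads 12.2.3 is told to keep following her. These can be reconciled, but the section that sites act on should not need reconciling.
- **Treatment.** The switch is automatic and one-sided. The arms differ only in concentration (8.1, Tables 1 and 2). A standard-arm violator moves from trial standard dose to non-trial standard dose, so her regimen is unchanged. A high-dose violator loses the allocated dose.

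Switches that clinical care requires are properly part of the intention-to-treat effect. Switches made only because 8.7 says so are avoidable, and they bias the comparison toward no difference. For CS that means a loss of power. For tachysystole and hyperstimulation it would make the high dose look somewhat safer than it is, and assessing its safety is a stated secondary objective (6.3).

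**Working it through.** **Inputs from the protocol.** 1,500 women allocated 1:1, so 750 per arm (8, 12.1). Two-sided tests at 0.05 (12.1, 12.2). CS 32% v 24%, or the same 25% relative reduction from 24%, which is 24% v 18% (12.1). Tachysystole 17% v 23% and hyperstimulation 11% v 16% (10.2.2).

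**Input not in the protocol.** The share *f* of the high-dose arm switched because of a violation. No rate is given, and 8.7 expects few. I use 2%, 5% and 10% as illustrations: 15, about 38 and 75 of 750 women.

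**Method.** Normal approximation with pooled variance and no continuity correction:

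power = Φ[(|p₁ − p₂| − 1.96 × SE₀) / SE₁]

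where SE₀ = √[2p̄(1 − p̄)/n], SE₁ = √[p₁(1 − p₁)/n + p₂(1 − p₂)/n] and p̄ is the mean of p₁ and p₂.

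**Step 1: reproduce the plan.** For 32% v 24% at 90% power the formula gives 660 per arm, 1,320 in all, as stated in 12.1. For 24% v 18% with 750 per arm, SE₀ = 0.02103 and SE₁ = 0.02098, so (0.06 − 1.96 × 0.02103)/0.02098 = 0.895 and power is 81.5%; 12.1 states 80%. For safety, 10.2.2 says "we would have 80% power to detect an absolute increase of 6% in the rate of tachysystole"; the formula gives 82.8%, and 80.9% for hyperstimulation. The plan's figures hold.

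**Step 2: apply the switch.** The worst case is that a switched woman changes from the start and takes the full standard-dose risk. She stays in the intention-to-treat set. The high-dose risk becomes

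p₂′ = (1 − f) × p₂ + f × p₁

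For CS at 24% v 18% with f = 5%: 0.95 × 0.18 + 0.05 × 0.24 = 0.183. The relative risk moves from 0.75 to 0.183/0.24 = 0.763. Then SE₀ = 0.02109, SE₁ = 0.02104, and (0.057 − 1.96 × 0.02109)/0.02104 = 0.745, so power is 77.2%.

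| Outcome (standard v high) | f = 0 | 2% | 5% | 10% |
|---|---|---|---|---|
| CS 24% v 18% | 81.5% | 79.8% | 77.2% | 72.4% |
| CS 32% v 24% | 93.3% | 92.3% | 90.6% | 87.2% |
| Tachysystole 17% v 23% | 82.8% | 81.4% | 79.1% | 74.9% |
| Hyperstimulation 11% v 16% | 80.9% | 79.5% | 77.2% | 73.0% |

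The CS relative risk moves from 0.75 to 0.755, 0.763 and 0.775 in both CS scenarios.

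**Step 3: what the fix could recover.** If half of the switches are avoidable (an assumption), f is halved to 1%, 2.5% and 5%. CS power at 24% v 18% is then 80.6%, 79.4% and 77.2%, a gain of 0.8, 2.2 and 4.8 points over the 2%, 5% and 10% columns.

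**The case against.** The strongest reply has four parts.

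1. **Follow-up is already secured.** This stands. Sections 12.2, 12.2.3 and 8.7's own intention-to-treat sentence settle it. A reader might infer from 8.7 that violators leave the analysis or are no longer followed; the documents do not support that. What is left is a conflict of wording.

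2. **Labour data are not shown to be lost.** This also largely stands. A reader might infer that tachysystole, hyperstimulation and dose data go missing for violators, because the table starts labour data at study treatment and 8.1 mentions only the randomised drug. But that rests on one table row and a form that is not in the documents. The row runs until after birth, so it covers a woman switched after starting. Section 8.3 provides for continuous fetal monitoring whenever oxytocin is used and for documentation of tachysystole and hyperstimulation, and 11.1 has most outcomes transcribed from routine records and missing items chased. The residue is small: a woman withdrawn before the infusion starts, and no stated rule for recording non-trial oxytocin, although total and maximum dose are process outcomes (9.2).

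3. **Standard dose is the prudent default.** The high arm may reach 64 mU/min, against a recommended maximum of 20 mU/min in the appended product information. Violations near the start of treatment, such as reaching full dilation, may well call for stopping. This is fair, and the proposed wording keeps that fallback. It does not justify a switch where no such reason exists, and 8.7 draws no such line. It is also true that 12.2.3 names deviations and violations separately while 8.7 names only violations, so 8.7 need not catch every minor lapse; but with the term undefined, each site must decide.

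4. **The size is assumed.** True. No violation rate is documented, and 8.7 expects timing to keep violations few.

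**Conclusion.** The point holds as a minor one, confined to the automatic switch and the wording around it. Followed as written, 8.7 removes the dose contrast for high-dose violators only, and nothing else in the protocol lets their allocated treatment continue.

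The cost is small at low violation rates. At an assumed 2% switched, CS power falls by 1.7 points at 24% v 18% (81.5% to 79.8%) and by 1.0 point at 32% v 24% (93.3% to 92.3%). The lower-rate scenario matters because it set the target of 1,500, and its margin over 80% is gone at about 2%. In the 32% scenario power is still 87.2% at 10%. All of these are upper bounds for the given *f*: they assume a switch from the start, no remaining effect of high-dose exposure and the full standard-dose risk.

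A reader might infer that the trial is underpowered or needs more women. The documents do not support that: the stated sample sizes reproduce, and the loss depends on a rate that nobody has stated.

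**What to change.** In 8.7, limit withdrawal from the trial to the woman's own decision, and add:

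> A protocol violation is recorded but does not by itself withdraw a woman or end follow-up (see 12.2.3). Allocated trial treatment continues unless there is a safety, eligibility or clinical reason to stop it, in which case non-trial standard-dose oxytocin is given.

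As a minor clarification, state in the data collection table that Labour-form collection runs from randomisation and includes the dose of any non-trial oxytocin.

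The cost is one paragraph, one table row and a reminder to sites. The sample size, the analysis and the woman's right to leave are unchanged.
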